### 1.4.1.2 Clinical pharmacodynamics

Rapid, sustained, and significant dose-dependent decreases were seen in alanine aminotransferase (ALT), aspartate aminotransferase (AST), gamma glutamyl transferase (GGT), and alkaline phosphatase (ALP) at levels predictive of histologic improvement (see Table 1). Both doses showed significant reductions in N-terminal type 3 collagen propeptide (Pro-C3) and enhanced liver fibrosis (ELF) score (both total score and individual components) supporting an effect on fibrogenesis. High -sensitivity C-reactive protein (hsCRP) significantly decreased by 52% with 600 mg, in conjunction with improvements in glycemic control and key atherogenic lipoproteins. There were no changes in weight or body mass index (BMI), suggesting a treatment effect independent of weight loss. Liver fat content was unchanged with both doses, consistent with the icosabutate mechanism of action.

 Table 1.
 Placebo-Adjusted Absolute Changes in Non-Invasive Biomarkers

Biomarker (Unit)	Icosabutate 300 mg (n=33)	Icosabutate 600 mg (n=35)
ALT (U/L)	-19*	-25.4*
AST (U/L)	-9.4#	-13.5#
GGT (U/L)	-16.9#	-28.6*
ALP (U/L)	-12.7*	-19.6*

Table 1. Placebo-Adjusted Absolute Changes in Non-Invasive Biomarkers (Continued)

Biomarker (Unit)	Icosabutate 300 mg (n=33)	Icosabutate 600 mg (n=35)
Bilirubin (mg/dL)	-0.0	-0.14#
Pro-C3 (ng/mL)	-4.5*	-4.6*
ELF	-0.4#	-0.6*
hsCRP (mg/L)	-1.2	-2.3#
HbA1c (%)	0.0	-0.3
HOMA-IR	-1.5	-2.1
LDL-C (mg/dL)	5.5	-3.9
HDL-C (mg/dL)	3.2#	2.3
Remnant-C (mg/dL)	-6.1#	-8.0*
ApoC3 (mg/dL)	-1.6#	-2.7*
TG (mg/dL)	-27.1#	-34.0#

\* = p < 0.001, # = p < 0.05

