## Discontinue study drug if:

- ALT or AST >8 × ULN
- ALT or AST >5 × ULN for >2 weeks
- ALT or AST >3 × ULN and TBL >2 × ULN or INR >1.5
- ALT or AST >3 × ULN with the appearance of fatigue, nausea, vomiting, right upper quadrant pain or tenderness, fever, rash, and/or eosinophilia (>5%)

AND follow the patient until resolution of signs/symptoms.

ALT = alanine aminotransferase; AST = aspartate aminotransferase; INR = international normalized ratio; TBL = total bilirubin; ULN = upper limit of normal.

Suspected drug-induced liver injury monitoring in patients with normal liver transaminases and bilirubin at baseline should be performed throughout the study according to the procedures summarized below.

- If patients with normal baseline liver indices develop elevations of aspartate aminotransferase (AST) or alanine aminotransferase (ALT) >2 × upper limit of normal (ULN) or total bilirubin (TBL) >1.5 × ULN values during the study, repeat testing should be performed within 48 hours.
  - o If there are persistent elevations (ALT or AST >2 × ULN or TBL >1.5 × ULN) upon repeat testing, close observation (testing and physical examination 2 to 3 times per week) should be implemented. An important purpose of the close observation is to gather additional clinical information to seek other possible causes of the observed liver test abnormalities, such as one of the following: acute viral hepatitis, alcoholic and autoimmune hepatitis, hepatobiliary disorders, cardiovascular causes, or concomitant treatments. Discontinuation of study drug should be considered.
- Study drug should be discontinued, and the patient should be followed until resolution of signs or symptoms, in the following situations:
  - $\circ$  ALT or AST >8 × ULN.
  - $\circ$  ALT or AST >5 × ULN for more than 2 weeks.
  - $\circ$  ALT or AST > 3 × ULN and (TBL > 2 × ULN or international normalized ratio [INR] > 1.5).
  - $\circ$  ALT or AST >3 × ULN with the appearance of fatigue, nausea, vomiting, right upper quadrant pain or tenderness, fever, rash, and/or eosinophilia (>5%).

For any patients who present with a constellation of syndromes indicative of liver disease as per the Investigator's overall assessment (ie, fatigue, nausea, vomiting, right upper quadrant pain or tenderness, fever, rash, and/or eosinophilia [>5%]), perform liver function tests to determine if liver disease is worsening and discontinue the study drug if worsening is confirmed.

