# Discontinue study drug if:

- Baseline average measurements were <2 × ULN and ALT or AST increases to >5 × baseline measurements
- Baseline average measurements were ≥2 × ULN (but <5 × ULN) and ALT or AST increases to >3 × baseline measurements
- Baseline average measurements were ≥5 × ULN and ALT or AST increases to >2 × baseline measurements
- ALT or AST increase >2 × baseline average measurements AND the increase is accompanied by a concomitant increase in TBL to >2 × baseline average measurements or the INR concomitantly increases by >0.2

AND follow the patient until resolution of signs/symptoms.

ALT = alanine aminotransferase; AST = aspartate aminotransferase; INR = international normalized ratio; TBL = total bilirubin; ULN = upper limit of normal.

Suspected drug-induced liver injury monitoring in patients with elevations in liver transaminases or bilirubin at baseline should be performed throughout the study according to the procedures summarized below.

- If patients with abnormal baseline liver indices develop elevations of AST or ALT >2 × baseline average or TBL >1.5 × baseline average values during the study, repeat testing should be performed within 48 hours.
  - o If there are persistent elevations (ALT or AST >2 × baseline average or TBL >1.5 × baseline average values) upon repeat testing, then close observation (testing and physical examination 2 to 3 times per week) should be implemented and discontinuation of study drug should be considered.
- Discontinue the study drug if any of the following occur:
  - o Baseline average measurements were  $<2 \times ULN$  and ALT or AST increases to  $>5 \times baseline$  measurements.
  - O Baseline average measurements were  $\geq 2 \times \text{ULN}$  (but  $< 5 \times \text{ULN}$  as per eligibility requirements) and ALT or AST increases to  $> 3 \times \text{baseline}$  measurements.
  - o Baseline average measurements were  $\geq 5 \times \text{ULN}$  and ALT or AST increases to  $\geq 2 \times \text{baseline}$  measurements.
  - o ALT or AST increase >2 × baseline average measurements AND the increase is accompanied by a concomitant increase in TBL to >2 × baseline average measurements or the INR concomitantly increases by >0.2.

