3.1.2 Analysis Visits

Scheduled visits will be assigned to analysis visits as recorded on the electronic case report form (eCRF). Unscheduled and early termination visits will be assigned to analysis visits according to the visit windows described in the following table:

Analysis Visit	Target Analysis Day	Low Analysis Day	High Analysis Day
Visit 2 (Week 0)	1	NA	NA
Visit 3 (Week 4)	28	2	49
Visit 4 (Week 10)	70	50	91
Visit 5 (Week 16)	112	92	140
Visit 6 (Week 24)	168	141	196
Visit 7 (Week 32)	224	197	252
Visit 8 (Week 40)	280	253	322
Visit 9 (Week 52)	364	323	371
Visit 10 (Week 54) Safety FUP	378	372	

If there is more than one assessment within a visit window, then the analysis visit will be assigned by the following priorities:

- 1. Use the assessment from the visit with the matching visit label.
- 2. Use the visit closest to the target visit day; in the case of ties, use the earlier visit.

Further details of analysis visit assignment will be provided in the Analysis Data Model (ADaM) Specifications

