3.1.4 Summary Statistics

Categorical data will generally be summarized with counts and percentages of patients. The denominator used for the percentage calculation will be clearly defined. Continuous data will generally be summarized with descriptive statistics including n (number of non-missing values), mean, standard deviation, median, Q1, Q3, minimum, and maximum.

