3.6.2 Clinical Laboratory Tests

Fasting Hematology, biochemistry, coagulation and lipid panels and urinalysis will be collected at all study visits. A list of laboratory tests to be performed is included in Protocol Appendix B.

Descriptive statistics of each clinical laboratory parameter will be presented for baseline values and for values and the change and percent change from the baseline at each post-baseline visit by treatment group and overall.

Values outside the normal range will be categorized as High (i.e., above the normal range) or Low (i.e., below the normal range) based on the central laboratory's normal reference range. The number and percentage of patients with values outside the normal range will be summarized by parameter for baseline and for each post-baseline visit.

Shift tables will also be presented for baseline versus maximum-baseline values and baseline versus minimum post-baseline values.

All safety laboratory data will be presented in patient listings.

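### SAP 3.6.2 categorises liver tests only as High or Low, so no laboratory-derived table compares the arms on the Appendix E liver criteria

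*SAP*

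**What the plan says.** SAP 3.6.2 gives one categorisation for laboratory values: "Values outside the normal range will be categorized as High (i.e., above the normal range) or Low (i.e., below the normal range", with the central laboratory's reference range as the standard. It also summarises the values themselves and "the change and percent change from the baseline at each post-baseline visit by treatment group and overall". SAP 3.1.4 defines such summaries as "descriptive statistics including n (number of non-missing values), mean, standard deviation, median, Q1, Q3, minimum, and maximum". SAP 3.6.2 then states: "Shift tables will also be presented for baseline versus maximum-baseline values and baseline versus minimum post-baseline values". It does not name the shift categories or say whether unscheduled samples count towards the extremes. All safety laboratory data are listed by patient.

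Protocol Appendix E is written in other terms. For patients with normal baseline tests it uses multiples of ULN, in places with a duration, such as "ALT or AST >5 × ULN for >2 weeks", or together with bilirubin or INR. For patients elevated at baseline it uses multiples of the patient's own baseline, such as "Baseline average measurements were <2 × ULN and ALT or AST increases to >5 × baseline measurements". In both groups an elevation calls for a repeat within 48 hours and, if it persists, testing 2 to 3 times a week.

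SAP 3.1.2 places unscheduled samples in visit windows. When a window holds more than one assessment, the first priority is: "Use the assessment from the visit with the matching visit label".

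SAP 2.3.6 names suspected drug-induced liver injury as the event of special interest. SAP 3.6.1 counts such events by arm.

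**The concern.** The safety tables and the liver monitoring plan do not share a scale. Appendix E asks how far a value rose, from what starting point, for how long, and whether bilirubin or INR rose with it. The SAP's categories ask only whether a value lies outside the normal range. Protocol Inclusion Criterion 7 admits ALT and AST up to just under 5 x ULN, and Appendix E has a full pathway for elevated baselines. The plan therefore expects some patients to be High before the first dose, and for them the category cannot change upwards.

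At stake is the arm comparison for the one named organ risk, in a trial whose secondary objective in the protocol is safety and tolerability. A reader of the report would have to rebuild from listings how many patients in each arm crossed each Appendix E level. The SAP does this kind of tabulation elsewhere: section 3.6.5 counts patients by QTcF above 450, 480 and 500 msec and by increases above 30 and 60 msec.

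**Working it through.** The plan gives no figure to reproduce here. The check applies the SAP's rules to values at Appendix E levels.

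**1. Categories.** High means above 1 x ULN. The shift table is assumed to use these categories, since SAP 3.6.2 defines no others. The baseline and peak values below are illustrations.

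| Baseline (x ULN) | Peak (x ULN) | Peak / baseline | Appendix E level passed | Shift cell |
|---|---|---|---|---|
| 1.5 | 1.3 | 0.87 | none | High to High |
| 1.5 | 7.6 | 5.07 | >5 x baseline (baseline <2 x ULN) | High to High |
| 2.5 | 7.6 | 3.04 | >3 x baseline (baseline 2 to <5 x ULN) | High to High |
| 4.5 | 13.6 | 3.02 | >3 x baseline (baseline 2 to <5 x ULN) | High to High |
| 0.8 | 2.1 | 2.62 | >2 x ULN (repeat test) | Normal to High |
| 0.8 | 8.1 | 10.12 | >8 x ULN (stopping level) | Normal to High |

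Three rises past a stopping level share a cell with a small fall. From a normal baseline, a repeat-test trigger and a stopping level also share a cell.

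**2. How many patients.** The documents do not give the share above ULN at baseline. As an assumption only, for any one test: 20%, 50% or 80% of 88 patients is 88 x 0.2 = 18, 88 x 0.5 = 44 or 88 x 0.8 = 70 per arm who could not show a new High.

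**3. Means.** One patient rising from 1.5 to 9 x ULN moves the mean of an 88-patient arm by (9 - 1.5)/88 = 0.085 x ULN. Mean change and the repeated-measures model in SAP 3.4.2.3 will not reveal a single case.

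**4. Repeat tests.** Take a scheduled visit on its target day and a repeat 2 days later. Days left in the window = upper limit - (target + 2). Further tests = days left x 2/7 to days left x 3/7.

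| Visit | Target | Upper limit | Days left | Further tests in window |
|---|---|---|---|---|
| 3 | 28 | 49 | 19 | 5.4 to 8.1 |
| 4 | 70 | 91 | 19 | 5.4 to 8.1 |
| 5 | 112 | 140 | 26 | 7.4 to 11.1 |
| 6 | 168 | 196 | 26 | 7.4 to 11.1 |
| 7 | 224 | 252 | 26 | 7.4 to 11.1 |
| 8 | 280 | 322 | 40 | 11.4 to 17.1 |
| 9 | 364 | 371 | 5 | 1.4 to 2.1 |

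In every row the 48-hour repeat falls in the same window as the labelled sample, so the labelled value is tabulated and the repeats are not. The triggering scheduled value stays in. Scheduled treatment visits are 4 to 12 weeks apart, so a criterion that lasts more than 2 weeks depends heavily on the samples left out.

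**5. Reference values.** Protocol 8.7 accepts local laboratory tests for suspected liver injury, while SAP 3.6.2 categorises against the central range. Parts of Appendix E refer to a baseline average, while SAP 3.1.3 uses one predose value. The current tables could therefore not be reread as Appendix E counts.

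**The case against.** The strongest reply is that liver injury is visible elsewhere. At a scheduled visit, the patient going from 1.5 to 7.6 x ULN appears as a +407% change and probably as that arm's maximum. Protocol 8.1 makes an abnormality that requires action on study drug an adverse event, and Protocol 8.1.4 makes suspected liver injury an event of special interest. SAP 3.6.1 counts these events, and events leading to discontinuation of study drug, by arm. Listings hold every safety value. The SAP also matches Protocol 9.2.2, which plans abnormalities against normal ranges.

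Most of this stands, and it rules out the reading that the SAP cannot show liver injury at all. It does not supply the missing comparison. A maximum is one value per test and visit, with no patient count and no pairing with bilirubin or INR. Event tables rest on investigator reports. Listings are not a by-arm summary.

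A reader might also infer that repeat tests are discarded. They are displaced only when a labelled sample exists, they remain in listings, and for the shift-table maximum the SAP is silent.

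A further tempting inference starts from Protocol 1.4.1.2: "Rapid, sustained, and significant dose-dependent decreases were seen in alanine aminotransferase (ALT), aspartate aminotransferase (AST". If ALT falls on drug, criteria set against pre-treatment baseline might seem to favour the active arms. The documents do not establish this. Baseline multiples apply only to patients elevated at baseline, and for a given baseline the triggering level is the same in every arm. Any size would need individual baselines that the documents do not give. It would also be a comment on Appendix E, not on SAP 3.6.2.

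**Conclusion.** The point holds as a reporting gap common to the SAP and Protocol 9.2.2. The SAP has no laboratory-derived by-arm count of patients meeting the Appendix E criteria and no joint table of ALT/AST with bilirubin or INR. Its High/Low categories cannot grade a rise in a patient already High. Repeat tests are left out of by-visit tables when a labelled sample exists, and it is not stated whether they enter the shift-table maximum.

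The loss of grading is certain for any patient above ULN at baseline on the test in question. How many patients that is cannot be said from the documents. The conclusion assumes that the shift tables use the High/Low categories and that the ADaM specifications, which SAP 3.1.2 cites for further visit-assignment detail and which were not available, do not already settle the handling of repeats. The documents do not support saying that the safety objective cannot be answered. The change is worth making because it is cheap and puts the main monitored risk on its own scale.

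**What to change.** Add to SAP 3.6.2, by arm, using all post-baseline results in the database, including unscheduled, early-termination and any local results, each against its own laboratory's ULN:

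- **Appendix E counts.** Number and percentage of patients ever meeting each criterion, separately for normal and elevated baseline. Use the baseline average where Appendix E does, and state how it is derived.
- **Graded shift tables.** ALT, AST and total bilirubin, baseline against worst post-baseline value, in ULN bands built from Appendix E's own cut-points (for ALT and AST: 2, 3, 5 and 8 x ULN). Including baseline separates patients who entered at a level from those who worsened to it.
- **Concurrent elevations.** Count of patients with ALT or AST elevated together with bilirubin or INR, as Appendix E defines them for each baseline group.

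Also state that the shift-table extremes include unscheduled samples, and correct maximum-baseline to maximum post-baseline.

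The cost is a few added safety tables from results already in the database. No Appendix E threshold, visit or conduct rule changes.

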3.6.3 Vital Signs

Vital signs will be measured at all study visits. Vital signs parameters include blood pressure, heart rate and body temperature. Three replicate blood pressure readings will be taken at each visit and the average of these measurements will be used in the analysis.

Vital signs parameters will be summarized by visit, treatment group and overall. Change and percent change from baseline at each post-baseline visit will be presented for each parameter.

All vital sign data will be presented in patient listings.

3.6.4 Anthropometric measures

Height is measured at the Screening Visit only. Weight will be measured at each study visit. BMI will be derived for each study visit using the weight measured at that visit and the height measured at the screening visit. Anthropometric data will be summarized by visit, treatment and overall. Change from baseline at each post-baseline visit will be presented for weight and BMI.

All anthropometric data will be presented in patient listings.

3.6.5 Electrocardiograms

Single 12-lead ECGs will be performed at Screening, Visit 2 (Week 0), Visit 5 (Week 16), Visit 7 (Week 32), Visit 9 (Week 52), and at the Safety Follow-up or ET Visit. ECG parameters include Heart Rate, PR Interval, QRS Duration, QT Interval, QTcF Interval and RR Interval.

ECG parameters will be summarized by visit, treatment group and overall. Change and percent change from baseline at each post-baseline visit will be presented for each parameter.

Additionally, the number and percentages of patients in each treatment group will be provided with QTcF in the following categories:

- Absolute values:
 - QTcF Interval > 450 msec
 - QTcF Interval > 480 msec
 - QTcF Interval > 500 msec
- Change from baseline:
 - QTcF increase from baseline > 30 msec
 - QTcF increase from baseline > 60 msec

Overall interpretation will also be summarized by visit.

All ECG data will be presented in patient listings.

3.6.6 Physical Examinations

Full physical examinations (including general appearance; eyes, ears, nose, and throat; head and neck; chest and lungs; cardiovascular; abdomen; musculoskeletal; lymphatic; dermatological; neurological systems; mental status; and extremities) will be performed at Screening; Visit 2 (Week 0), Visit 9 (Week 52) and at the Safety Follow-up or ET Visit. Abbreviated physical examinations will be performed at all other study visits.

All physical examination data will be listed.

4 DATA SAFETY MONITORING COMMITTEE

An external, independent Data Safety Monitoring Committee (DSMC) was to review all available unblinded preliminary safety and biomarker results, as described in the DSMC Charter. The DSMC Charter describes the overall guidelines, composition and roles, and responsibilities of the independent DSMC, timing of meetings, methods of providing information to and from the DSMC, frequency and format of meetings, data analysis recommendations, and DSMC relationships with other parties participating in the conduct of this study. Patient accrual continued throughout the period of the DSMC review. The DSMC was to advise on the accrual of the remaining patients per protocol or any amendments that are necessary for safety reasons.

Patients, investigators, site staff and in general all personnel directly involved in the conduct of the study were to remain blinded to the patients' treatment assignment until the completion of the study.

5 ANALYSIS TIMING

5.1 Interim Analysis

An interim analysis was planned for this study after 90 patients had completed 16 weeks of treatment. This analysis was reviewed by the DSMC according to the DSMC Charter. The conclusions and recommendations of the DSMC were shared blindly with the Sponsor and clinical sites. A separate interim analysis plan was finalized prior to conducting the interim analysis.

5.2 Pre-Final Analysis

After the database is locked and exclusions from analysis populations have been finalized, the randomized treatment assignments will be unblinded and the pre-final analysis will be generated. Pre-final tables, figures and listings (TFLs) will be provided approximately 3 weeks after database lock.

5.3 Final Analysis

After all comments on the pre-final analysis have been resolved and the study database is declared final, the final analysis will be generated. Final TFLs will be provided approximately 1 week after the study database is declared final. If there were no changes to the pre-final analysis or the study database, the pre-final TFLs may be considered final. In addition to TFLs, SDTM data and ADaM data along with associated files will be provided. Associated files may include: annotated CRFs, Standard Data Tabulation Model (SDTM) specifications, SDTM programs, ADaM specifications, ADaM programs, TFL programs, and Clinical Data Interchange Standards Consortium (CDISC) Define packages for both SDTM and ADaM data.

6 CHANGES FROM PROTOCOL-SPECIFIED STATISTICAL ANALYSES

The planned changes to the protocol-specified statistical analyses, as detailed in this SAP are:

- Key secondary efficacy endpoints added for different definitions of response fibrosis improvement and resolution of NASH with fibrosis improvement.
- cT1 demoted to exploratory endpoint (from secondary) as there is uncertainty over clinical significance.
- The primary population for all efficacy analysis updated to mITT Population, with all analyses to be repeated for the ITT Population.
- No imputation to be performed for the continuous secondary endpoints.
- ALP added to list of liver enzymes to be analyzed as secondary endpoints.

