### 5.3 Randomization and Blinding

This study follows a randomized, double-blind, placebo-controlled design. Patients will be randomized via the Interactive Response Technology (IRT) system to 1 of 3 parallel treatment groups at Visit 2 (Week 0) in a 1:1:1 ratio. Patients will be stratified by biopsy fibrosis score (2 levels: F1 versus F2 or F3). Randomization information will be concealed from the Investigators and the patients until the end of the study, with the exception of an emergency situation involving a patient that requires unblinding of the treatment assignment.

Both NST-4016 and placebo will be provided as capsules for oral administration and will be identical in appearance.

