# 9.2.1 Analysis of Efficacy

The efficacy analysis will be performed on the ITT Population; missing values for continuous endpoints will be imputed using multiple imputation methods.

Baseline will be defined as the value at the Screening Visit for measurements from the liver biopsy and imaging data and as the predose value at Visit 2 (Week 0) for the biomarker data. For other efficacy endpoints, baseline will be defined as the predose value at Visit 2 (Week 0); if this value is missing, then the latest predose value will be used.

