# 9.2.1.1 Primary efficacy analysis

The primary endpoint (ie, the percentage of patients with resolution of NASH without worsening fibrosis) will be analyzed using the ITT Population. Patients without a Week 52 (or ET, if applicable) liver biopsy will be imputed as nonresponders. The number and percentage of patients meeting the criteria for the primary endpoint will be summarized by treatment group.

The primary analysis will be conducted using the data from the 600 mg NST-4016 and placebo groups using the Cochran-Mantel-Haenszel test, stratified by biopsy fibrosis score (2 levels: F1 versus F2 or F3). The primary analysis will be based on the use of a 2-sided test at the alpha=0.05 level of significance.

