2.2.2 Sample Size Determination

A sample size of 88 patients per treatment group provides 80% power to detect a treatment effect of 22% (40% responder rate for active versus 18% placebo), assuming a dropout rate of 25%.

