3.2.2 Intent-to-Treat (ITT) Population

The ITT Population will include all patients who were randomized and received at least 1 dose of study drug.

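### Without imputation, the ITT repeat of the histology ANCOVAs uses essentially the mITT patients, so agreement between the two says nothing about missing biopsies

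*SAP*

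**What the plan says.** - Protocol Section 9.2.1 analyses efficacy in the ITT Population and states that "missing values for continuous endpoints will be imputed using multiple imputation methods".
- SAP Section 6 changes both parts. The primary efficacy population becomes mITT, "with all analyses to be repeated for the ITT Population", and a separate item reads "No imputation to be performed for the continuous secondary endpoints". A reason is given for demoting cT1, but none for removing the imputation.
- SAP Section 3.1.6 says the same in general form. A missing biopsy counts as nonresponse for the primary endpoint; all other data are analysed as available.
- SAP Section 3.2.2: "The ITT Population will include all patients who were randomized and received at least 1 dose of study drug". Section 3.2.3 narrows this to mITT by requiring a valid baseline biopsy and a valid second biopsy. The second is valid if taken within 90 days of the last dose or Week 52 visit.
- SAP Section 3.4 runs every efficacy analysis in mITT and again in ITT, with a per-protocol repeat for the primary and secondary endpoints.
- SAP Section 3.4.2.2 analyses change from baseline to Week 52/ET in NAS, its components, fibrosis and the composite score by ANCOVA on treatment, fibrosis stratum and baseline score.
- Protocol Section 6.5 allows a biopsy at early termination only after at least 6 months on study drug.

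**The concern.** Moving from ITT to mITT restricts the analysis to patients who came back for a biopsy. A reader will naturally look to the ITT repeat to see whether that restriction matters. For the histology change scores it cannot answer the question, because the patients whose absence is at issue are absent from both runs. Two near-identical tables labelled mITT and ITT could then be taken as evidence that missing biopsies are harmless.

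Missingness also need not be unrelated to treatment. Patients who leave before 6 months have no second biopsy by design. The interim safety summary (Protocol Section 1.4.1.3) reports mild nausea in 4.3%, 9.0% and 21.3% of the placebo, 300 mg and 600 mg groups. The documents do not link nausea to dropout, so this is a reason to examine the matter and not evidence of bias.

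**Working it through.** **1. The plan's own figure.** Inputs:
- Two-sided alpha of 0.05 (Protocol Section 9.2.1.1: "The primary analysis will be based on the use of a 2-sided test at the alpha=0.05 level of significance").
- 88 per arm, 80% power, 40% versus 18%, 25% dropout (SAP Section 2.2.2).
- Allocation "to 1 of 3 parallel treatment groups at Visit 2 (Week 0) in a 1:1:1 ratio" (Protocol Section 5.3).

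With pooled variance and no continuity correction:

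n = [1.960 × √(2 × 0.29 × 0.71) + 0.842 × √(0.40 × 0.60 + 0.18 × 0.82)]² / 0.22² = 65.6, rounded up to 66 per arm.

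66 / 0.75 = 88, and power at 66 per arm is 80.2%. The stated sample size reproduces, and it treats 25% of patients as unevaluable.

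**2. Which patients enter each run.** As an illustration, let the planned 25% stand for patients with no second biopsy: 264 × 0.25 = 66, or 22 per arm, leaving 264 − 66 = 198 with both biopsies.

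| Run | Patients in the set | Patients with a change score |
|---|---|---|
| mITT, no imputation | 198 | 198 |
| ITT, no imputation (SAP) | 264 | 198 |
| ITT, multiple imputation (protocol) | 264 | 264 |

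The first two rows fit the same model to the same 198 patients. In simulated trials the estimates and standard errors were identical.

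**3. The 90-day exception.** The validity rule stands in the mITT definition, whereas Section 3.1.6 uses data as available, so a late second biopsy could enter the ITT run only. If k of the 198 are late, the ITT run has 198 patients and mITT has 198 − k. The documents give no k. A simulation (300 trials per value, assumed residual SD of 1.5 NAS points, assumed dose effects, late and missing biopsies at random) gave:

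| Assumed k | Mean absolute shift in the 600 mg estimate, NAS points |
|---|---|
| 0 | 0.00 |
| 3 | 0.03 |
| 5 | 0.03 |
| 10 | 0.05 |
| 20 | 0.07 |

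The standard error was about 0.26 throughout. Any such shift tests the window rule. The 66 patients with no biopsy stay out whatever k is.

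**4. What could be hidden.** Let m be the fraction without a second biopsy, equal in each arm, and suppose no treatment difference among them. Then all-patient difference = (1 − m) × completer difference + m × 0, so completer / all-patient = 1 / (1 − m).

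| Assumed m | 1 / (1 − m) | Completer difference larger by |
|---|---|---|
| 10% | 1 / 0.90 = 1.11 | 11% |
| 15% | 1 / 0.85 = 1.18 | 18% |
| 25% | 1 / 0.75 = 1.33 | 33% |

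**5. What each imputation would show.** Multiple imputation within arm, using only the ANCOVA covariates, assumes missing at random and returns essentially the completer estimate. It moves only through extra predictors such as Week 16 markers, which patients leaving before Week 16 lack at that visit. Imputing missing active-arm patients from the placebo distribution pulls the estimate towards (1 − m) times the completer difference, which is the scenario in step 4.

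**The case against.** - **Low stakes.** SAP Section 3.1.5 places these scores outside the six-hypothesis sequence and declares their p-values nominal. This stands and limits the weight of the point, though the estimates and intervals will still be reported and read.
- **The ITT repeat works elsewhere.** For the primary endpoint it counts patients without a biopsy as nonresponders. In the repeated-measures marker models and for MRI-PDFF, patients without a second biopsy can still contribute. This stands: although "No imputation to be performed for the continuous secondary endpoints" covers all continuous secondary endpoints, the difficulty is confined to histology.
- **The change is disclosed.** It is listed in Section 6. But disclosure supplies no method, and no other section gives one for these scores. The per-protocol set is a subset of mITT, and the sensitivity ANCOVA using baseline ballooning changes a covariate, not the patients.
- **A safeguard that fails.** A reader might infer that the SAP offers the ITT repeat as its robustness check. It says only that the analyses will be repeated; the purpose is not stated.
- **Runs that cannot differ.** This is too strong because of the 90-day window. Late biopsies should be few on the normal schedule: dosing continues up to 30 days for a delayed Visit 9 biopsy (Protocol Section 5.5.3), and early termination visits follow promptly. However, the COVID-19 measures in Appendix G let Visit 9 be replaced by telehealth or a home visit.
- **A quarter of patients absent, and an estimate one third too large.** The documents support neither as fact. The 25% is a planning dropout rate. Patients leaving after at least 6 months on drug are due a biopsy and stay in the Week 52/ET analysis, while some completers may have none. The one-third figure needs the full 25%, equal missingness and no difference among the missing.

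**Conclusion.** The point holds for the ANCOVAs of NAS, the individual histological scores and the composite score. With no imputation, the ITT and mITT runs use the same patients, apart from any with a second biopsy outside the 90-day window. Their agreement carries no information about missing biopsies.

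The possible consequence is 11%, 18% or 33% inflation of the completer difference at an assumed 10%, 15% or 25% missing, with equal missingness by arm and no treatment difference among the missing. These are scenarios for dropout bias, which the two coinciding runs would fail to reveal; they are not predictions. No confirmatory claim depends on these endpoints, so this is a worthwhile inexpensive improvement and not a threat to the trial's main conclusion.

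**What to change.** Leave the available-case ANCOVA in mITT as it is. For the ITT repeat of the histology ANCOVAs only:

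1. Run a placebo-based multiple imputation, which tests the no-benefit scenario directly.
2. Alongside it, run the multiple imputation the protocol specifies, by arm, with baseline score, fibrosis stratum and whatever Week 16 markers are available (for example ALT, Pro-C3, ELF and MRI-PDFF) as predictors. The protocol names no predictors, so this list is a suggestion.
3. State whether a second biopsy outside the 90-day window enters the ITT run.
4. Amend SAP Sections 3.1.6 and 6 to match.

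The cost is one imputation program, two extra tables and somewhat wider ITT intervals. No new data are needed.
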